7.2.4. Change from hospital discharge in clinic visit trough FEV₁

Change from hospital discharge in clinic visit trough FEV₁ will be derived only for participants who were hospitalised for their index exacerbation and who have been subsequently discharged.

Change from hospital discharge in clinic visit trough FEV₁ measured post-bronchodilator is defined as:

FEV₁ measured prior to dosing and post-bronchodilator on Day X – FEV₁ measured post-bronchodilator and prior to dosing on day of hospital discharge.

Where Day X is 14, 28, 56 and 84.

Change from hospital discharge in clinic visit trough FEV₁ measured pre-bronchodilator is defined as:

FEV₁ measured prior to dosing and pre-bronchodilator on Day X – FEV₁ measured prior to dosing and post-bronchodilator on day of hospital discharge.

Where Day X is 14, 28, 56 and 84.

Note, as per Section 5.1 of the Protocol, if discharge takes place between Day 11 and Day 17 (inclusive), the assessments planned for Day 14 may be completed on the day of discharge. In these cases, for this endpoint only, the FEV₁ assessment will be assigned the hospital discharge assessment and the Day 14 assessment will be missing. Refer to Section 13.2.1.1 for further details.

In addition, if discharge takes place after Day 14, the Day 14 assessment will be missing for this analysis.

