7.2.4.1. Statistical analyses

Change from hospital discharge in clinic visit trough FEV₁ will be analysed using a repeated measures analysis as described in Section 7.1.2 if there are a sufficient number of participants to provide a meaningful analysis, otherwise the data will be summarised.

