13.2. Appendix 2: Assessment Windows

13.2.1. Definitions of Assessment Windows for Analyses

13.2.1.1. Hospital discharge

As per Section 5.1 of the Protocol, if discharge takes place between Day 11 and Day 17 (inclusive), the assessments planned for Day 14 may be completed on the day of discharge. In these cases, for this endpoint only, the FEV₁ assessment will be assigned the hospital discharge FEV₁ assessment and the Day 14 assessment will be missing.

For all other analyses and summaries that include participants who were hospitalised for their index exacerbation, an additional Analysis Timepoint of “HOSPITAL DISCHARGE” will be derived. However, in the cases where discharge takes place between Day 11 and Day 17 (inclusive), participants will be summarised under DAY 14 and a footnote to say that participants who were discharged at Day 14 are summarised under DAY 14 will be included.

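### For discharge after Day 14, Section 7.2.4 drops only the Day 14 visit, so a Day 28 FEV₁ taken on or before the day of discharge still counts as a change from discharge

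*SAP*

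**What the plan says.** SAP Section 7.2.4 restricts the endpoint to "participants who were hospitalised for their index exacerbation and who have been subsequently discharged". It sets no upper limit on the day of discharge. The post-bronchodilator change is FEV₁ at the visit minus FEV₁ "measured post-bronchodilator and prior to dosing on day of hospital discharge". The pre-bronchodilator change also subtracts a post-bronchodilator reference, "measured prior to dosing and post-bronchodilator on day of hospital discharge". For both, the visits are fixed by "Where Day X is 14, 28, 56 and 84", with no condition that the visit falls after discharge.

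Two provisions remove a visit, and both concern Day 14:

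- Discharge on Days 11 to 17, with the Day 14 assessments done that day: the FEV₁ "assessment will be assigned the hospital discharge assessment and the Day 14 assessment will be missing".
- Later discharge: "if discharge takes place after Day 14, the Day 14 assessment will be missing for this analysis".

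Section 13.2.1.1 covers the same ground for Day 14 ("if discharge takes place between Day 11 and Day 17 (inclusive), the assessments planned for Day 14 may be completed on the day of discharge") and says nothing on Days 28, 56 or 84 for this endpoint. Under Section 7.2.4.1 the endpoint "will be analysed using a repeated measures analysis as described in Section 7.1.2 if there are a sufficient number of participants", and is otherwise summarised. The repeated measures model, which is set out in Section 7.1.3, takes in every scheduled visit after baseline.

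**The concern.** The endpoint is meant to describe what happens after a participant leaves hospital. The authors saw that a visit on or before discharge cannot serve that purpose, because they exclude Day 14 when discharge is later. The same reasoning applies at every scheduled visit, but the rule stops at Day 14. Naming one visit and staying silent on the other three invites a programmer to keep those three.

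For a stay that runs past the Day 28 visit, the derived Day 28 value is an in-hospital FEV₁ minus a later discharge FEV₁. Improvement between the two is then recorded as decline. These values come from the longest stays and sit in the same column as genuine post-discharge changes. If there are too few participants for the model, they still enter the descriptive summary.

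**Working it through.** The plan states no figure to reproduce here. The check applies the Section 7.2.4 rules literally to a range of discharge days.

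**Inputs.** From Section 7.2.4: visits at Days 14, 28, 56 and 84; Day 14 removed for discharge on Days 11 to 17 (taking the Day 14 assessments as done at discharge) and for discharge after Day 14; no other removal. Nominal visit days are used, and actual visit dates would move the boundaries by a few days.

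| Day of discharge | Visits kept by 7.2.4 | Kept, but before discharge | Kept, but on day of discharge | Visits strictly after discharge among those kept |
|---|---|---|---|---|
| up to 10 | 14, 28, 56, 84 | none | none | 14, 28, 56, 84 |
| 11–27 | 28, 56, 84 | none | none | 28, 56, 84 |
| 28 | 28, 56, 84 | none | 28 | 56, 84 |
| 29–55 | 28, 56, 84 | 28 | none | 56, 84 |
| 56 | 28, 56, 84 | 28 | 56 | 84 |
| 57–83 | 28, 56, 84 | 28, 56 | none | 84 |
| 84 | 28, 56, 84 | 28, 56 | 84 | none |

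The rules work for discharge up to Day 27. From Day 28 on, at least one kept visit is not after discharge.

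**Reversed order (assumed values).** Discharge on Day 35, with post-bronchodilator FEV₁ of 1.25 L at Day 28 and 1.40 L at discharge. The plan's formula gives 1.25 − 1.40 = −0.15 L at Day 28, although FEV₁ rose by 1.40 − 1.25 = 0.15 L between the two measurements.

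**Same day (assumed values).** Discharge on Day 28, with one assessment serving as visit and discharge value: post-bronchodilator 1.40 − 1.40 = 0. The pre-bronchodilator change is not zero, because its reference is the post-bronchodilator value. With a pre-bronchodilator FEV₁ of 1.28 L it is 1.28 − 1.40 = −0.12 L.

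**Scale (assumptions only).** Section 3.1 times Interim Analysis 1 at about 50 severe among 170, and 50/170 = 29%. Section 7.1.3 equates severe with hospitalised. The following are assumed and not in the SAP: 1000 randomised, 1–3% of hospitalised participants discharged at or after the Day 28 visit, and a small arm holding 1/11 of participants.

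- Hospitalised: 1000 × 50/170 ≈ 294.
- Affected overall: 1–3% of 294 ≈ 3 to 9.
- Hospitalised in a small arm: 294/11 ≈ 27, so expected affected 27 × 1–3% ≈ 0.3 to 0.8.
- One value of −0.2 L (assumed) among 27, the other changes averaging zero: 0.2/27 ≈ 0.007 L, about 7 mL.

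**The case against.** The best reply is that the case may hardly arise. It needs an index stay reaching the Day 28 visit, and the SAP has no length-of-stay data. The arrangement for combining discharge with a visit comes from Protocol Section 5.1, which is not at hand, so it cannot be seen whether participants still in hospital at Day 28 are assessed then. The endpoint's name and the Day 14 provision make the intent clear, and a careful programmer would probably extend it. No decision depends on the result: the endpoint is absent from the Interim Analysis 1 and 2 lists in Section 3.1, and its tables are due only at the final reporting stage. Section 13.4.2 also provides in general terms for assessing major departures from scheduled visit days.

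Most of this stands as a limit on size. It does not close the gap, since Sections 7.1.3, 7.2.4.1 and 13.2.1.1 nowhere restrict the later visits, and the general provision in 13.4.2 sets no rule for this derivation. Intent shown for one visit does not replace a rule for the other three.

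A reader might also infer that the change is always zero when discharge falls at a visit. That holds only post-bronchodilator and only when one measurement serves as both values, a sharing that the SAP describes only for Days 11 to 17.

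**Conclusion.** The rule as written gives wrong values for index stays reaching the Day 28 visit. A Day 28 visit before discharge yields a change with reversed time order, opposite in sign to recovery if FEV₁ rose up to discharge. A Day 28 visit that supplies the discharge measurement yields a post-bronchodilator change of zero.

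This is a minor point. The number affected is not given and is probably few, and the effect is confined to one secondary endpoint in the hospitalised subset, shown in Tables 2.19 to 2.21.

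Two stronger readings are tempting and not supported. One is a material distortion of the Day 28 result. The counts and the 7 mL shift above rest on assumed sample size, late-discharge share, arm size and FEV₁ error, and even then less than one affected participant is expected in a small arm. The 29% is the mix planned for the first interim, and Section 3.1 allows the stratification proportions to be changed afterwards. The 75 mL threshold in Section 7.1.2 belongs to the primary endpoint and is no benchmark for this one. The other is that all later visits are exposed alike. Day 56 and Day 84 are reached only by index stays of about 8 and 12 weeks.

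**What to change.** Keep the provision for discharge on Days 11 to 17. Replace the last sentence of Section 7.2.4 with: *Any scheduled assessment (Day 14, 28, 56 or 84) performed on or before the day of the hospital discharge assessment is set to missing for this analysis.* Put the same wording in Section 13.2.1.1, limited to this endpoint.

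The cost is one sentence in two places and one date comparison in the program. Nothing changes for discharge on Days 18 to 27. For discharge on Days 28 to 55 the usable visits become Days 56 and 84, for Days 56 to 83 only Day 84, and from Day 84 on none. No valid post-discharge measurement is lost.

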7.2.4.1. Statistical analyses

Change from hospital discharge in clinic visit trough FEV₁ will be analysed using a repeated measures analysis as described in Section 7.1.2 if there are a sufficient number of participants to provide a meaningful analysis, otherwise the data will be summarised.

7.2.5. EXacerbations of Chronic Pulmonary Disease Tool - Patient Reported Outcome (EXACT)

The EXACT is a 14-item daily diary designed to provide a measure of patient-reported symptoms of COPD exacerbation. An EXACT Total Score, ranging from 0 to 100, where

higher scores indicate a more severe condition, will be derived for each day of diary collection according to the instructions in the EXACT User Manual (Version 8.0, [Evidera, 2016](#)).

The electronic EXACT diary does not allow a study patient to skip individual items, therefore no missing data are expected for individual items. However, if missing values occur for individual items, the Total Score that contains the item will be set to missing for that day. Moderate-to-severe COPD patients are expected to experience symptom(s) each day, and a score of zero on all 14 EXACT items is likely to represent a situation where in order to complete the diary quickly, the respondent did not accurately report their daily symptom(s), therefore if the EXACT Total Score is 0, it will be set to missing.

A 3-day Rolling Average EXACT Total Score will be calculated for each day, X, as:

$$\frac{(\text{EXACT Total Score on Day X-1} + \text{EXACT Total Score on Day X} + \text{EXACT Total Score on Day X+1})}{(\text{Number of days with non-missing values})}$$

Note, for Day 1, the Rolling Average EXACT Total Score will be calculated as the average of EXACT Total Score on Days 1 (Randomisation) and 2 only, since no EXACT data is collected prior to randomisation. Similarly, the Rolling Average EXACT Total Score for the last study day will be calculated as the average of EXACT Total Score on the last day and on the day before the last day.

The Rolling Average EXACT Total Score will be calculated for each day as long as at least 1 EXACT total score in the sequence is present. Therefore, only in the case where EXACT total scores are missing for 3 consecutive days in a row (or 2 consecutive days in the case of the first and last day rolling average calculation), will the rolling average score be missing.

The Maximum Observed Value (MOV) is defined as the highest Rolling Average EXACT Total Score observed within the first 14 days of randomisation. Note: this definition differs from the definition in the EXACT User Manual of "the highest rolling average EXACT score observed in the context of an EXACT exacerbation within the first 14 days of the exacerbation", since the date of the index exacerbation is likely to be prior to randomisation.

7.2.5.1. Proportion of participants achieving EXACT-defined recovery from index exacerbation

EXACT-defined recovery from the index exacerbation is defined as a decrease in the Rolling Average EXACT Total Score ≥ 9 points from the Maximum Observed Value, sustained for ≥ 7 days, with the first of the 7 days defined as the recovery day.

The proportion of participants achieving EXACT-defined recovery from the index exacerbation by Days 14, 28, 56, and 84 will be calculated as:

$$\frac{(\text{Number of participants who experience an EXACT-defined recovery on or before Day X})}{(\text{Total number of participants in the MITT population})}$$

Where Day X is 14, 28, 56, and 84.

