3. PLANNED ANALYSES

3.1. Interim Analyses

Ongoing data reviews of unblinded safety data, conducted by an Internal Safety Review Committee (iSRC), will be performed throughout the trial. Details will be documented in the iSRC charter.

Interim analyses of the primary endpoint and key secondary endpoints to inform internal decision making will be conducted periodically throughout the trial. The first analysis (Interim Analysis 1) is planned to occur when approximately 170 participants complete 28 days of treatment, where approximately 50 of the 170 participants have an index exacerbation defined as severe. A change that could arise from this interim analysis is a specification of the stratification proportions by index exacerbation severity status (moderate or severe). This decision will be based on inspection of all available endpoints at the interim analysis.

Further interim analyses will be performed, depending on the observed recruitment rate. At least one interim analysis of the primary endpoint of change from baseline in clinic visit trough FEV₁ at Day 84 measured post-bronchodilator will be performed to

determine whether or not any adjustments to the randomization ratio across doses would help optimize the characterization of the dose response profile for nemiralisib. This analysis (Interim Analysis 2) is planned to occur when approximately 300 participants complete 84 days of treatment or when approximately 400 participants remain to be randomized, whichever occurs first. Adjustments could include ceasing randomization to an existing dose(s) of nemiralisib and/or modification of the allocation ratios for the existing nemiralisib doses and/or addition of a 25mcg dose. Other changes may include specification of the stratification proportions by index exacerbation severity status.

An interim analysis of efficacy and safety data collected during the Double-Blind Treatment Period will be conducted when the last participant in the study has completed the 12-week Double-Blind Treatment Period (End of Treatment Interim Analysis). The aim of this analysis is to provide GSK with timely data to inform internal decision making, prior to the end of study.

The following table describes the endpoints that will be analysed/summarised at each interim:

Interim	Purpose of interim	Endpoints

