Interim Analysis 1	To inform internal decision making	
 • Change from baseline in FEV₁ at Days 14, 28, and 56 measured pre- and post-bronchodilator • Other spirometry measures (percent predicted FEV₁, Forced Vital Capacity (FVC), percent predicted FVC and FEV/FVC ratio • On-treatment exacerbations • Proportion of participants achieving EXACT-defined recovery by Days 14, 28, 56 and 84

Interim	Purpose of interim	Endpoints
Interim Analysis 2	To determine if any adjustments to the randomization ratio would help characterize the dose response profile for nemiralisib	Endpoints listed for Interim Analysis 1 and also: 
 • Change from baseline in FEV₁ at Day 84 measured pre- and post-bronchodilator • Rate of (on-treatment) exacerbations over the 12-Week Treatment Period • Time to next (on-treatment) exacerbation during the 12-Week Treatment Period • Proportion of responders using the CAT • Change from baseline in CAT Total Score • Proportion of responders using the SGRQ • Change from baseline in SGRQ Total Score • Rescue medication use, as measured in eDiary
End of Treatment Interim Analysis	To inform internal decision making	Selected Efficacy and Safety endpoints as defined in Appendix 11: List of Data Displays

The statistical methods of analyses are described in Section 7.

The Respiratory Data Sciences Group will apply machine learning techniques to the interim data to determine if identifiable phenotypic sub-population(s) of COPD participants are present at baseline, and if they result in different responses to Nemiralisib, to predict which participants will respond to Nemiralisib therapy, and to identify/quantify relationship(s) between different endpoints and response measures. Details of these analyses will be described in a separate RAP and results will be reported separately to the Clinical Study Report (CSR).

The following functions will be unblinded to interim analysis data: Clinical Statistics, Clinical Programming and Respiratory Data Sciences Group. Other member of GSK will be unblinded to group level summary data following the interim analyses (as documented internally).

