3.1.1. Futility analyses

At least one interim analysis for futility will be performed. The first analysis will occur at Interim Analysis 2, i.e. when 300 participants complete 84 days of treatment, or when approximately 400 participants remain to be randomized, whichever occurs first.

Futility will be assessed in a sequential manner.

- 1) Futility will first be assessed for the primary endpoint of change from baseline in FEV₁ at Day 84 by fitting a suitable dose response model, as described in Section 7.1.2.
- 2) If the posterior predictive probability of declaring success for this endpoint is low across all doses, then futility will be assessed for the rate of (on-treatment) exacerbations endpoint.
- 3) If the posterior predictive probability of declaring success for this endpoint is low, then the study may be stopped.

Any decision to stop will be made after a review of all the data summarised/analysed at the time of the interim, including the proportion of participants achieving the EXACT-defined recovery.

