4. ANALYSIS POPULATIONS

Population	Definition / Criteria	Analyses Evaluated
All Participants Enrolled (APE) Population	
 All participants who are screened for eligibility. 	
 Study Population
Modified Intent To treat (MITT) Population	
 All randomized participants who receive at least one dose of study treatment. Participants will be analyzed according to the treatment that they were randomized to. 	
 Study Population Efficacy
Per Protocol (PP) Population	
 All randomized participants who receive at least one dose of study treatment, excluding any participants with an important protocol deviation. Participants will be analyzed according to the treatment that they were randomized to. 	
 Sensitivity analyses of efficacy
Safety Population	
 All randomized participants who received at least one dose of study treatment. Participants will be summarised according to the treatment that they actually received. 
 If participants receive >1 treatment, then they will be summarised according to the most frequently dosed treatment. In cases where the frequency is equal, the participant will be assigned the lowest dose strength of nemiralisib 	
 Safety
Pharmacokinetic (PK) Population	
 All participants in the Safety population who had at least 1 non-missing PK assessment (Non-quantifiable [NQ] values will be considered as non-missing values). Participants will be summarised according to the treatment that they actually received 	
 PK

Refer to [Appendix 11](#): List of Data Displays which details the population used for each display.

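### At Interim Analyses 1 and 2 the EXACT recovery proportion is divided by the whole MITT population, so participants not yet followed to Day X and not yet recovered count as failures, mainly at Days 56 and 84

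*SAP*

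**What the plan says.** Section 7.2.5.1 defines the proportion as "Number of participants who experience an EXACT-defined recovery on or before Day X" divided by "Total number of participants in the MITT population", with X equal to 14, 28, 56 and 84. Section 4 defines MITT as "All randomized participants who receive at least one dose of study treatment", with no minimum follow-up.

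Section 3.1 lists "Proportion of participants achieving EXACT-defined recovery by Days 14, 28, 56 and 84" among the Interim Analysis 1 endpoints, carries these endpoints into Interim Analysis 2, and refers to Section 7 for methods. Interim 1 falls "when approximately 170 participants complete 28 days of treatment". Interim 2 falls when about 300 participants "complete 84 days of treatment or when approximately 400 participants remain to be randomized, whichever occurs first". Appendix 11 puts the EXACT recovery tables on MITT: 2.15 and 2.16 at Interim 1 (summary only, by programming note) and 2.26 and 2.27 at Interim 2 (odds ratios). No text gives a different denominator for the interims.

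Section 3.1.1 says that any decision to stop follows a review of all the interim data, "including the proportion of participants achieving the EXACT-defined recovery". Section 3.1 says that the severity stratification proportions may be set after Interim 1, on inspection of all available endpoints.

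**The concern.** The formula suits a cohort whose members have all reached Day X. At an interim with recruitment open, some of MITT have not. Those who have already had a confirmed recovery are counted correctly. The others enter the denominator as failures although their Day X status is unknown.

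The lag is longer than X days. Recovery must hold for 7 days starting on the recovery day (7.2.5.1), and the rolling average in 7.2.5 is centred, so it uses the following day's score. A recovery on Day X is fully confirmed only at about Day X+7.

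Elsewhere the SAP separates observed from pending participants. The FEV1 predictive probability in 7.1.2 distinguishes those with Day 84 data from those yet to be observed, and time to recovery in 7.2.5.2 is censored. The recovery proportion has no such provision. At stake is how to read a figure that is reviewed before any stop at Interim 2 and is among the endpoints inspected at Interim 1.

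**Working it through.** The SAP states no expected recovery rate or accrual rate, so there is no figure of its own to reproduce. The triggers, the formula and the confirmation lag come from the SAP. All other inputs are assumptions: steady accrual of r = 1 or 2 participants per day, no withdrawals, final recovery p = 65% on placebo and 75% on active, and mean recovery time τ = 10 or 20 days.

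**Share of MITT whose Day 84 status can be confirmed** (randomised at least 84 + 7 = 91 days before the cut-off):

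- Interim 1: MITT = 170 + 28r = 198 (r = 1) or 226 (r = 2). Confirmable: (198 − 91)/198 = 54%, or (226 − 182)/226 = 19%.
- Interim 2, trigger of 300 completing 84 days: MITT = 300 + 84r = 384 or 468. Confirmable: (384 − 91)/384 = 76%, or (468 − 182)/468 = 61%.

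**Displayed proportion.** True recovery by day t is F(t) = p(1 − exp(−t/τ)). The displayed value is the mean over MITT of F(min(X, follow-up − 7)), and F is zero when follow-up is under 7 days.

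Worked case: Interim 2, r = 2, τ = 20, X = 84. Follow-up is spread evenly over 468/2 = 234 days.

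- Over 91 days: weight 143/234 = 0.611, placebo F(84) = 0.640.
- 7 to 91 days: weight 84/234 = 0.359, mean F = 0.65 × [1 − (20/84)(1 − exp(−84/20))] = 0.498.
- Under 7 days: contributes zero.
- Placebo total: 0.611 × 0.640 + 0.359 × 0.498 = 0.570, against a true 0.640.
- Active, scaled by 75/65: 0.658, against a true 0.739.
- Odds ratio: 1.45, against a true 1.59.

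**All days.** Ranges cover both accrual rates and both recovery times:

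| Day | True placebo | Shown, Interim 1 | Shown, Interim 2 | True odds ratio | Odds ratio shown, Interim 2 |
|---|---|---|---|---|---|
| 14 | 33-49% | 29-46% | 31-47% | 1.25-1.35 | 1.24-1.34 |
| 28 | 49-61% | 41-56% | 45-59% | 1.35-1.52 | 1.32-1.48 |
| 56 | 61-65% | 48-59% | 55-62% | 1.52-1.61 | 1.42-1.54 |
| 84 | 64-65% | 49-59% | 57-62% | 1.59-1.61 | 1.45-1.54 |

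Within a scenario, the placebo shortfall in percentage points is:

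- Interim 2: about 1-3 at Day 14, 2-4 at Day 28, 3-6 at Day 56 and 3-7 at Day 84.
- Interim 1: about 2-5, 4-8, 5-13 and 6-15 respectively.

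**Second check, different assumptions.** Take true Day 84 recovery of 60% versus 70% (odds ratio 1.56), exponential recovery times, and a share u of MITT not yet at Day 84 with follow-up uniform over 0-84 days. The table would show 57.0% versus 66.7% (odds ratio 1.51) at u = 10%, 52.6% versus 61.7% (1.46) at u = 25%, and 45.2% versus 53.5% (1.40) at u = 50%. The direction is the same.

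**Other Interim 2 trigger.** The Interim 2 figures above apply to the first trigger. If about 400 remaining to be randomised comes first, the look is earlier and a larger share of MITT is incompletely followed. The SAP gives no total sample size from which to compute that case.

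**The case against.** The strongest reply is that nothing formal depends on this figure. Futility under 3.1.1 and 3.1.1.1 is sequential: predictive probability must be low for FEV1 across all doses and then also for the exacerbation rate. A reader might infer that the denominator could itself stop the trial. The SAP does not support that, because EXACT recovery is supporting information with no threshold. With follow-up balanced across arms, the odds ratio moves toward 1 but does not change direction. If there were 50 to 110 participants per arm (an assumption), the Interim 2 Day 84 shift would be about 0.1 to 0.3 posterior standard deviations of the log odds ratio.

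Other stronger readings also go too far:

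- **Odds ratios at Interim 1.** None is planned; Tables 2.15 and 2.16 are summary only.
- **The rule works only at the final analysis.** The End of Treatment analysis is run once the last participant has completed 12 weeks, so incomplete follow-up is essentially gone, apart from the few days needed to confirm very late recoveries.
- **A spurious dose effect.** With 10% versus 30% of two arms incompletely followed and the same true recovery of 65%, an odds ratio of 0.77 would appear. But the SAP places changes of allocation after Interim 2 and gives no reason to expect such imbalance before it.
- **A distorted moderate/severe comparison.** This would need one stratum to have been recruited later than the other, which the SAP does not suggest.

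Finally, Example Shell 9 has an n row under each day, separate from the column N, and 7.2.5.4 fits a separate model at each time point. A programmer might use a smaller denominator. That n is undefined, however, and using it that way would contradict 7.2.5.1. It is a reason to clarify the text and does not override the formula.

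**Conclusion.** The point holds for Interim Analyses 1 and 2. Followed as written, 7.2.5.1 understates recovery by Day X because unknown status is scored as failure. The effect is small at Days 14 and 28 at Interim 2, somewhat larger at those days at Interim 1, and greatest at Days 56 and 84. For Day 84, the displayed placebo recovery is 49-59% at Interim 1 and 57-62% at Interim 2 against a true 64-65%, and the Interim 2 odds ratio is 1.45-1.54 against 1.59-1.61. These sizes rest on the assumed accrual, recovery rates and recovery times, and for Interim 2 on the first trigger. The direction does not depend on the particular values, provided follow-up is balanced across arms.

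No formal decision rule uses the proportion. It should still be corrected, because the SAP names it for the stopping review and it is among the endpoints inspected at Interim 1.

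**What to change.** In 7.2.5.1, state that at Interim Analyses 1 and 2 the numerator and denominator for Day X, and the corresponding logistic model in 7.2.5.4, include only MITT participants randomised at least X+7 days before the data cut-off, including those who withdrew. Selection is on randomisation date alone, so it does not depend on outcome. Define the n row of Example Shell 9 to match.

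The cost is one sentence and a date filter in the interim programs. The downside is a smaller n at later days: for Day 84, about 44 to 107 participants at Interim 1 and 286 to 293 at Interim 2 across all arms, under the accrual assumptions above. Dropping Days 56 and 84 from the Interim 1 tables is optional once the filter is in place.
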